5.15	AirPurge System Disposable Cartridge Storage	13

Anesthesia Safety Products - Confidential Information

This document and the subject matter contained herein is the property of Anesthesia Safety Products and may not be copied, reproduced, or disclosed to others without the expressed written permission of a duly authorized agent of the company.

5.16	Cleaning and Maintenance	13
5.17	Device Returns	13
6.0	Study Procedure	13
6.1	Schedule of Events	13
6.2	Eligibility Checklist / Demographics	14
6.3	Operative Report	14
6.4	Data Monitor	15
7.0	Statistical Plan	15
8.0	Safety Issues	16
8.1	AirPurge System Indicator Lights / Alarms	16
8.2	Protocol Deviations, Device Complaints and Reportable Events	16
8.3	Definitions	16
8.4	Medical Monitoring	17
9.0	Data Handling and Record Keeping	17
9.1	Confidentiality	17
9.2	Case Report Forms (CRFs) and Source Documents	17
9.3	Records / Materials to be Maintained	18
10.0	Administrative Information	18
10.1	Investigator Selection and Qualifications	18
10.2	Informed Consent Process (Optional)	18
10.3	Institutional Review Board (IRB) (Optional)	19
10.4	Protocol Amendments	19
10.5	Subject Identification (ID) Number	19
11.0	Training and Monitoring	19
11.1	Data Monitoring	19
11.2	Clinical Site Monitoring / Training	19
11.3	Safety Monitoring	20
12.0	Publication	20
13.0	References	20
---	Attachment 1 – Schedule of Events	21

Anesthesia Safety Products - Confidential Information

This document and the subject matter contained hereon is the property of Anesthesia Safety Products and may not be copied, reproduced, or disclosed to others without the expressed written permission of a duly authorized agent of the company.

A. List of Abbreviations:

AirPurge	AirPurge Air Detection and Removal System
CRF	Case Report Form
I.V.	Intravenous
Kg	Kilogram
ml	Milliliters
RH	Relative Humidity
MDR	Medical Device Reporting
SIV	Site Initiation Visit

B. Post-approval Multi-center Study Summary

Title	AirPurge™ Air Detection and Removal System Post-approval Multi-center Clinical Protocol
Protocol Number	CS001-2
Methodology	Prospective, observational, single arm / non-randomized post-approval study design
Study Duration	6-8 weeks
Clinical Sites	Multi-center; up to 5-8 Clinical Sites
Objectives	To measure the amount of air removed from the intravenous (I.V.) line by the AirPurge System in a clinical setting and to measure the frequency and duration of the AirPurge purging mechanism activity in a clinical setting with standardization of the procedure, I.V. fluid and I.V. line.
Number of Subjects	50 Study Subjects per Clinical Site; 200 to 300 Study Subjects in Total
Primary Inclusion Criteria / Procedure	Intravenous Fluid or Blood Delivery in Pediatric and Adult Patient Populations Undergoing arterial septal defect closure, ballooning of coarctation, craniotomy, craniosynostosis, patent ductus arteriosus, (pda) closure, pulmonary artery stent deployment, pulmonary valve balloon dilatation, spinal fusion, scoliosis or cardiac surgery involving cardiopulmonary bypass
Commercially Available Device and Planned Use	AirPurge™ Air Detection and Removal System used to remove air from intravenous line
Statistical Methodology	Final data analysis will be presented in text, tables, and graphical representations including mean, standard deviation and range outcomes and a time analysis of AirPurge purging activity during the procedure

Anesthesia Safety Products - Confidential Information

This document and the subject matter contained herein is the property of Anesthesia Safety Products and may not be copied, reproduced, or disclosed to others without the expressed written permission of a duly authorized agent of the company.

1.0 INTRODUCTION

This document is a protocol for a human research post-approval study. This study is to be conducted in accordance with applicable Good Clinical Practice standards and individual Clinical Site research policies and procedures.

1.1 BACKGROUND

The AirPurge System is identified by the FDA as “an Intravascular Administration Set, Automated Air Removal System”. It was classified as a Class II device under the *De Novo* process (K080644) and cleared for release for commercial marketing on March 4th, 2014.

The AirPurge System is designed to:

- Detect & remove air bubbles automatically with practically unhindered I.V. flow
- Remove air bubbles during infusion rates as high as 400 ml/minute
- Remove air bubbles as small as 25 micro-liters at high or low flow rates
- Remove air automatically during surgical procedures from intravenous solutions, blood, and blood products in I.V. setups that have single or multiple bags
- Eliminate the need for time-consuming manipulation during in-line air bubble removal (and the adjunct possibility of needle sticks).

1.2 COMMERCIALY AVAILABLE DEVICE

The *commercially available* Class II AirPurge Air Detection and Removal System is comprised of the AirPurge Device (control unit) and disposable Cartridge. In this protocol they are referred to as the AirPurge System, the Device or the Cartridge. The Device functions by:

- a) Detecting air in the intravenous (I.V.) line using software-controlled ultrasound sensing technology
- b) Diverting the flow in the I.V. line to the Collection Bag using a two pinch valve configuration, when air is detected, and
- c) Redirecting fluid back to the patient line after passage of the entrapped air.

The Device detects air in the I.V. line via two sensors (line-in and line to Collection Bag) and diverts flow into the Collection Bag. Flow to the patient is resumed when sensors indicate no air. Therefore, some of the I.V. fluid will be channeled to the Collection Bag during air removal. The volume of this I.V. fluid channeled to the Collection Bag is dependent on the I.V. flow rate and bubble configuration, (i.e., a discrete bubble or a string of connected bubbles).

Flow Rate	I.V. Fluid Volume Loss Per Purge
400 ml per minute	~7 ml
300 ml per hour	~0.1 ml

1.3 INTENDED USE & INDICATIONS FOR USE

The usage of the AirPurge System with Disposable Cartridge in conjunction with this post-approval clinical study will be in accordance with the Intended Use and Indications for Use from the AirPurge Operator’s Manual reviewed by FDA under *De Novo* K080644 (approval date: 3.4.2014).

Anesthesia Safety Products - Confidential Information

This document and the subject matter contained herein is the property of Anesthesia Safety Products and may not be copied, reproduced, or disclosed to others without the expressed written permission of a duly authorized agent of the company.

Intended Use: The AirPurge System is intended for the detection and automatic removal of air in intravenous lines during administration of blood, blood products and intravenous solutions.

Indications for Use: The AirPurge System is intended for the detection and automatic removal of air in intravenous lines during administration of blood, blood products, and intravenous solutions. It is indicated for use in the operating room and post anesthesia care areas. The AirPurge System is placed below I.V. bags using gravity feed or pressure, and may be used with or without fluid warmers.

1.4 PRECLINICAL DATA

De Novo K080644 which was approved by FDA on March 4, 2014 included the following preclinical supportive material: design FEMA, design functionality, sterilization and shelf life, biocompatibility, software verification and validation, electromagnetic compatibility / electrical safety, patient transport, cartridge internal clamp and overall device performance bench verification, validation and usability testing. The AirPurge System has been tested and found to be in compliance with IEC 60601-1-2 1994 medical device limits.

1.5 RISKS AND BENEFITS

1.5.1 RISK OF DEVICE

Use of the AirPurge System in this post-approval study represents no more than minimal to no additional risk beyond the routine use of intravenous (I.V.) fluid delivery since all Clinical Sites will be instructed to follow their standard of care visualization techniques for air bubble detection and removal *below* the AirPurge System and therefore there will be *no* modification in Clinical Sites' routine air bubble detection and removal procedures at the most distal end of the I.V. line closest to the patient; air filter usage if a standard of care will be placed *below* the AirPurge System. Clinical Sites will be trained on the proper use of the AirPurge including the importance of clearing the line *before* connection to the patient. Any boluses or critical medicine / contrast media delivery will be conducted *below* the AirPurge device. Risk mitigation will begin *prior to* study onset at each Clinical Site with a thorough review / Clinical Site personnel training on the recommended operating instructions provided in the AirPurge System Quick Operating Instructions and Operator's Manual including the Warnings and Caution sections from a risk related standpoint.

1.5.2 OTHER RISKS OF STUDY PARTICIPATION

No other risks of study participation have been identified since Clinical Sites will not be requested to modify their routine air bubble detection and removal procedures at the most distal end of the I.V. line closest to the patient.

1.5.3 POTENTIAL BENEFIT ANALYSIS

The AirPurge System provides automatic removal of air in intravenous (I.V.) lines during administration of intravenous solutions in the operating room and post anesthesia care areas. The major potential benefits include:

- Improved safety; reduced risk of venous air embolisms and associated complications (heart failure, stroke, extended recovery times, impaired cognition)
- Simple, hands free, auto purge, intuitive operation

Anesthesia Safety Products - Confidential Information

This document and the subject matter contained herein is the property of Anesthesia Safety Products and may not be copied, reproduced, or disclosed to others without the expressed written permission of a duly authorized agent of the company.

- Labor and attention saving convenience resulting from auto-purge function
- Reduced risk of clinician needle sticks while de-airing I.V. bags and lines
- Compatible with other infusion technologies, standard fluids, and flow rates.

2.0 STUDY OBJECTIVES

2.1 PRIMARY STUDY OBJECTIVES

The primary objectives of this post-approval clinical study are:

- 1) to measure the *amount of air removed from the intravenous (I.V.) line by the AirPurge System* in a clinical setting with standardization of the surgical procedure, I.V. fluid and flow rate
- 2) to measure the *frequency and duration of the AirPurge purging mechanism activity* in a clinical setting with standardization of the procedure, I.V. fluid and I.V. line.

3.0 STUDY DESIGN

3.1 GENERAL DESIGN

The AirPurge Air Detection and Removal System Post-Approval Multi-Center Clinical Study is a prospective, observational, single arm / non-randomized post-approval study design. This multi-center post-approval clinical study is *not* a comparative study design *nor* is the clinical design intended to support the functional safety and efficacy of the *commercially available* AirPurge System for the purposes of obtaining FDA approval. Therefore, there is *no* investigational device and *no* prospective safety / efficacy success criteria or endpoints. The AirPurge System will be utilized for the current FDA approved intended use / indications for use. The overall goal of this post-approval study is information gathering in regards to the clinical value of the AirPurge System within the operating room setting utilizing a set of controlled I.V. set-up parameters including I.V. fluid, I.V. line including the usage of key I.V. pole accessory equipment and a standardized group of procedures.

The study endpoint is the discontinuation of AirPurge System usage during the procedure and therefore there are *no* post-procedure follow-up requirements minimizing the risk of lost-to follow-up study subjects. Study subjects will be recruited from the Clinical Sites' current patient population scheduled to undergo one of the inclusion criteria procedures. Subjects will be enrolled into the study in a sequential manner.

Data collection is limited to two time points:

The hard copy CS001-12LL Eligibility Checklist / Demographics case report form (CRF) will be completed *prior to* surgery. Operative Day data will be collected utilizing two data collection methodologies as follows:

- 1) CS001-13LL Operative Report: This hard copy case report form (CRF) will be completed by Clinical Site personnel and collect information on device performance from the clinician's perspective, intravenous line fluid delivery specifics, and relevant background concerning the procedure.

Anesthesia Safety Products - Confidential Information

This document and the subject matter contained herein is the property of Anesthesia Safety Products and may not be copied, reproduced, or disclosed to others without the expressed written permission of a duly authorized agent of the company.

- 2) Data Monitor: The Data Monitor consists of hardware and software that are independent of and do *not* affect operation of the AirPurge device. The Data Monitor resides in the battery pack area of the AirPurge from which the batteries have been removed. The Data Monitor will collect objective data to measure 1) the *amount of air* removed from the intravenous line by the AirPurge, 2) the *frequency and duration of AirPurge mechanism activity* and 3) the *occurrence of any alarm conditions* in the AirPurge.

3.2 STUDY DURATION

Study duration is limited to the collection of preoperative eligibility criteria / baseline demographic information and procedure data. There are *no* post-procedure follow-up requirements for this post-approval study.

3.3 STUDY POPULATION

The study population for this post-approval clinical study will be comprised of up to 50 study subjects per Clinical Site with up to 5-8 participating Clinical Sites in total; 200-300 study subjects. Study Subjects will be drawn from Clinical Sites' pediatric and adult patient populations who are scheduled to undergo one of the following procedures: arterial septal defect closure, ballooning of coarctation, craniotomy, craniosynostosis, patent ductus arteriosus, (pda) closure, pulmonary artery stent deployment, pulmonary valve balloon dilatation, spinal fusion, scoliosis or cardiac surgery involving cardiopulmonary bypass.

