7.0 STATISTICAL PLAN

This multi-center post-approval clinical study is *not* a comparative study design *nor* is the clinical design intended to support the functional safety and efficacy of the AirPurge System for the purposes of obtaining FDA approval. Therefore, there are *no* prospective safety / efficacy success criteria or endpoints. The overall goal of this post-approval study is information gathering in regards to the clinical value of the AirPurge System utilizing a set of controlled I.V. set-up parameters and group of procedures.

All available data will be entered into standard Excel spreadsheets for analysis purposes and data entry verified *prior to* the final analysis. Planned data analyses include:

- 1) **CS001-12LL Eligibility Checklist / Demographics:** Data will be analyzed using standard demographic variable presentation for age, race, gender, height, weight and surface area and to record any pre-existing conditions (medical / drug) that could impact intravenous fluid delivery during the procedure.
- 2) **CS001-13LL Operative Report:** Data collected will be used to evaluate the clinical activity in the clinical setting to provide key background regarding the overall procedure, I.V. fluid delivery parameters and the operation of the AirPurge. Data will be presented for individual study subjects, as applicable and for the overall study population as a whole.
- 3) **Data Monitor:** The Study Sponsor will analyze the objective measurement data collected from the Data Monitor software and correlate Data Monitor measurements with the clinical data collected from Clinical Site personnel and documented on the CS001-13LL Operative Report. Analytical measurements will include:
 - Total volume of air captured (mean, range and SD) for individual study subjects and the overall study population as a whole)
 - Duration of AirPurge purge mechanism activity (mean, range and SD) for individual study subjects and the overall study population as a whole)
 - Frequency of AirPurge purge mechanism activity (mean, range and SD) for individual study subjects and the overall study population as a whole) to answer questions concerning the necessity of purging over the duration of a procedure (e.g. number of purging episodes; length of time between purging episodes)

Anesthesia Safety Products - Confidential Information

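### Do the planned 200–300 subjects contradict 50 per site at 5–8 sites?

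*Combined protocol and SAP*

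**What the plan says.** The enrolment figures appear in two places in the combined protocol and SAP.

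- **Section B, Post-approval Multi-center Study Summary.** The site count is "Multi-center; up to 5-8 Clinical Sites". The subject count is "50 Study Subjects per Clinical Site; 200 to 300 Study Subjects in Total". Here 50 per site carries no qualifier.
- **Section 3.3, Study Population.** The full statement is "up to 50 study subjects per Clinical Site with up to 5-8 participating Clinical Sites in total; 200-300 study subjects". Here both the per-site number and the number of sites are maxima.

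Section 7.0, Statistical Plan, derives no sample size. It disclaims any prospective "success criteria or endpoints. The overall goal of this post-approval study is information gathering", and it lists means, standard deviations and ranges for air volume, purge duration and purge frequency. Nowhere is the total presented as sites multiplied by subjects per site, and neither place says whether the site limit or the overall total ends enrolment.

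**The concern.** A reader who multiplies the summary's figures gets a range that disagrees with the stated total at both ends: 250 rather than 200, and 400 rather than 300. Working backwards, 200 subjects at 50 each need only four sites, while seven or eight full sites overshoot 300. With no rule on which figure governs, it is unclear when enrolment is complete.

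The possible stakes are the mix and number of sites. Warmer and filter use follow local practice (section 5.2), and section 7.0 reports results for the whole population. If a few large sites filled to 50 while others contributed little, the pooled summaries would mostly reflect those sites' habits and would be less precise than the headcount suggests.

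**Working it through.** **Inputs.** Per site: 50 (summary) or at most 50 (section 3.3). Sites: "up to 5-8 participating Clinical Sites in total". Total: "200 to 300 Study Subjects in Total". No alpha, power, effect size or precision target is given, so the only check is sites × subjects per site.

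**Step 1: try to reproduce the stated total with exactly 50 per site.**

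- 50 × 5 = 250 and 50 × 8 = 400. Against 200–300, the lower end differs by 50 and the upper end by 100, so the total is not reproduced.
- 200 / 50 = 4 and 300 / 50 = 6. The total is reproduced exactly by 4 to 6 full sites.

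**Step 2: read 50 as a ceiling, as section 3.3 does.** Average per site = total / sites.

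| Sites | Most possible (50 × sites) | Average needed for 200 | Average needed for 300 | Part of 200–300 attainable |
|---|---|---|---|---|
| 5 | 250 | 40.0 | 60.0 (over 50) | 200–250 |
| 6 | 300 | 33.3 | 50.0 | 200–300 |
| 7 | 350 | 28.6 | 42.9 | 200–300 |
| 8 | 400 | 25.0 | 37.5 | 200–300 |

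At every site count from 5 to 8, the per-site ceiling is compatible with a total inside the stated range. At 6 to 8 sites the whole range is attainable. At 5 sites the top of the range is out of reach, but a planning range need not be fully attainable at every site count.

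**Step 3: what the ambiguity could do to the results.** Ignoring site, the 95% half-width of a mean in standard deviation units is 1.96 / √n.

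- n = 200: 1.96 / 14.14 = 0.139
- n = 300: 1.96 / 17.32 = 0.113
- n = 400: 1.96 / 20 = 0.098

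The widest disputed span, 200 to 400, changes the half-width by 0.139 − 0.098 = 0.041 SD.

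**Step 4: allow for clustering by site.** The documents give no within-site correlation, so it is assumed here to lie between 0 and 0.05. For k sites of m subjects and n = 200, half-width = t(k − 1) × √{[1 + (m − 1) × correlation] / 200}.

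| Layout | t | Correlation 0 | Design effect at 0.05 | Correlation 0.05 |
|---|---|---|---|---|
| 4 × 50 | 3.182 | 0.225 | 3.45 | 0.418 |
| 5 × 40 | 2.776 | 0.196 | 2.95 | 0.337 |
| 8 × 25 | 2.365 | 0.167 | 2.20 | 0.248 |

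The number of sites matters more than the number of subjects. But 5 × 40 and 8 × 25 both satisfy section 3.3 as it stands, and would still satisfy it if the summary were aligned. Tidying the wording does not remove this difference.

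**The case for a change.** The best case for a change has three parts.

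**The two places state different rules.** True: the summary says 50 and section 3.3 says at most 50. A site reading only the summary might work towards 50, and seven or eight such sites would pass 300. This stands as a drafting inconsistency. The detailed section is the natural one to follow, and the sponsor issues each site's subject ID list (section 10.5) and monitors overall enrolment (section 11.2), so the total can be controlled in practice.

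**No rule says when enrolment ends, and other steps hang on it.** The Data Monitor is collected when a site finishes enrolling (section 6.1). That depends on each site being told it is finished, not on a formula linking the three figures. There is no hypothesis test whose error rate depends on the stopping point, and stopping at 220 or 290 for logistical reasons does not bias a mean or standard deviation. An observed range does tend to widen with more subjects, but that is true of any range and is readable from the n reported with it.

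**Few sites could dominate.** This is a fair point about interpretation, but a separate one. The 0.418 figure needs four sites and one assumed correlation. Scaling the site cap to the number of sites would not settle it neatly either: 42 at seven sites gives 7 × 42 = 294, 37 at eight gives 8 × 37 = 296, and 50 at five gives 250. A stop at 300 would then be reached only with six full sites. Lower caps would also be a new design restriction, not a correction of arithmetic.

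**Conclusion.** No change is needed. The multiplication behind the concern is correct, but it shows a contradiction only if every site enrols exactly 50, which section 3.3 does not say. Read as ceilings, the figures fit together: 200–300 at 6, 7 or 8 sites and 200–250 at 5.

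What remains is a missing qualifier in the summary, a loosely worded site count and an unstated order of precedence between site limit and total. The first two are clerical; the third is a gap that those running the study fill sensibly by treating 300 as the overall ceiling and 50 as the site ceiling. None of them alters the planned means, standard deviations and ranges, or how they are computed.

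This conclusion rests on the study staying descriptive, as section 7.0 describes it. If a precision target or a formal comparison were tied to the number of subjects, the enrolment limits would need to be fixed exactly.

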4.0 SUBJECT SELECTION AND WITHDRAWAL

4.1 INCLUSION CRITERIA

Potential study subjects meeting *all* of the following criteria will be considered suitable study subjects.

Male or female, any race

Pediatric or adult patient

- 1.0 Study Subject's weight is at least 5kg.
- 2.0 Study Subject scheduled to undergo one of the following procedures: arterial septal defect closure, ballooning of coarctation, craniotomy, craniosynostosis, patent ductus arteriosus, (pda) closure, pulmonary artery stent deployment, pulmonary valve balloon dilatation, spinal fusion, scoliosis or cardiac surgery involving cardiopulmonary bypass
- 3.0 Study Subject or acceptable parent / guardian is able to provide written informed consent, if Clinical Site requires

